4.2 Stopping and Dose Escalation Rule(s)

4.2.1 DLT at the Initial Dose after the First Infusion (Part I)

If the first subject experiences DLT at initial dose after first infusion, the trial will be halted, and the TITE-CRM will be updated accordingly. Reserve dose levels (-1 or -2) will be used based on the new information.

4.2.2 DLTs during the DLT Assessment Period at the First Dose Level (Part I)

A repeated dosing will be initiated at the first dose with the first subject if no DLTs have been observed during the observation period. The second subject in this cohort can be dosed with the same dose after three weeks of the initial dose (Figure 1) if the first subject did not experience DLT after the first infusion.

If one subject has DLT at the initial dose level during the DLT assessment period, recruitment to any cohort will be halted and the TITE-CRM will be updated with the new information and used to guide the decisions. Subjects in any cohort may continue receiving additional repeated doses if they have not experienced DLT while on repeated dosing and their accumulated time within the DLT assessment period will be taken into account by the TITE-CRM model.

4.2.3 Predefined Dose Escalation Rules for TITE-CRM (Part I)

Dose escalation is allowed to the next level after two subjects are treated with FP-1305 without DLT even if the full DLT assessment period is not completed. Dose escalation to further dose levels is not allowed until at least two subjects have been observed for the full DLT period. For example, dose escalation can be performed from dose level 0 to dose level 1 even if the full DLT period is not completed. However, dose escalation to level 2 is not allowed until two subjects have had the full 9-week DLT assessment either on level 0 or on level 1 and two subjects on level 1 has been dosed and followed up for a minimum of three weeks after the first dose. Similarly, the dose cannot be escalated from the third (Level 2) to the fourth level (Level 3) before the full DLT period of nine weeks is reached altogether from two previous dose levels (A. two subjects at the second (Level 1) dose level or B. two subjects at the third (Level 2) dose level or C. one subject at the second (Level 1) and one at the third (Level 2) dose level). New subjects will be enrolled to the particular dose level (Level 0, 1, or 2) to replace subjects that have not completed the full DLT of nine weeks at the first (Level 0), second (Level 1) or the third (Level 2) dose level. The enrolment of replacing subjects can be conducted without delays. If there is DLT in any subject at any level during the DLT assessment

period, no new subject will be dosed at any dose until the TITE-CRM has been updated. Dosing of the already dosed subjects may continue receiving additional repeated doses if they have not experienced DLT while on repeated dosing and TITE-CRM allows that. Recommendation from the TITE-CRM will be used to guide decisions on the dosing level of the next subject during dose escalation and to guide the MTD decision after completion of Part I. The third and the fourth subject at the highest dose level can be allocated into the trial when two subjects at this level have been observed for the full 9-week DLT period.

4.2.4 DLTs during the DLT Assessment Period after the Dose has been Escalated (Part I)

If the dose levels below the dose that demonstrate unacceptable DLT do not demonstrate DLT, the repeated dosing will be conducted at those dose levels. If an acceptable DLT level has been observed at the repeating dose levels, these levels are right doses for expansion cohorts from the DLT perspective. Immune function, PK and PD data will be used to determine if the dose is suitable for Part II. If none of the tested dose levels (including reserve dose levels -1 and -2 shown in [Table 4](#)) demonstrate acceptable safety, the trial will be halted until the Sponsor has amended the protocol or decided to stop the trial.

4.2.5 Delayed Toxicities That Occur after the Full DLT Assessment Period (For Part I subjects and Part II subjects that are in cohorts investigating new exposure levels)

Rules for enrolment halt are applied to all Part I subjects and in Part II to the first six study subjects in a cohort that is exploring a new level of exposure for the first time (i.e. Q2W and Q1W frequencies, and Q3W doses that have not been tested in Part I). This is to ensure the safety of the study subjects during dose exploration in case of potential AEs that occur after the defined DLT period, which could provide a signal to limit the dose. If two DLT evaluable subjects within a particular dose or dosing frequency i.e., in a specific dose escalation cohort have delayed AEs after the DLT assessment period, that would otherwise have been determined as DLTs during the period, enrolment to that cohort and all cohorts that have higher exposure is halted until the DMC has evaluated the cases and made the decision how to proceed. The rule applies only to a specific dose/cohort i.e., one delayed DLT in a cohort testing a certain level of exposure (dose & frequency) is not summed up with another delayed DLT from another dosing scheme. For example, one delayed DLT in 1 mg/kg Q1W and one delayed DLT in 10 mg/kg Q2W do not sum up to two delayed DLTs and contribute to this rule. In case two delayed DLTs occur in the first 6 subjects (DLT evaluable patients) at a particular dose e.g., at 10 mg/kg Q2W, the DMC meeting will be scheduled to evaluate has a maximum tolerated dose been achieved. Delayed DLT occurring beyond the first 6 subjects will be monitored, followed up and presented to the DMC during scheduled meetings. The enrolment halt described above refers to a temporary hold not to dose any new subjects at the dose level that is under DMC evaluation, or any higher dose level. Subjects already receiving the dose, or higher dose, that have not experienced a DLT may continue receiving the drug until DMC resolution or further guidance. Trial activities at lower doses are not affected and can continue as normal. As this enrolment halt is envisaged by the protocol, therefore no substantial amendment informing about the halt will be submitted in these situations. Further actions will be taken according to the DMC recommendation as necessary.

4.3 Dose Escalation to 30, 45 and 100 mg/kg Doses (Q3W, Part II)

Dose level 30 mg/kg and possibly 45 mg/kg and 100 mg/kg are included to investigate further tolerability, safety, receptor occupancy and efficacy in Part II of the study. 3 + 3 design (with additional safety margins/sentinel dosing between first three subjects) will be utilized to investigate these additional dose levels, and if tolerated, dose levels will be expanded to 10 subjects. To ensure safety at high doses the 30 mg/kg Q3W dose level will finish enrolment of all 10 subjects before the

dose can be escalated to 45 mg/kg Q3W. Similarly, the 45 mg/kg Q3W dose level will finish enrolment of all 10 subjects before the dose can be escalated to 100 mg/kg Q3W. These cohorts of ten patients exploring higher doses may consist of subjects with different cancer types of interest. Schedule of assessments in these dose levels is the same as Part II schedule (Table 2). In addition to standard Part II assessments the first three patients undergoing 45mg/kg and 100mg/kg will undergo 24h monitoring in hospital after the first dose.

4.3.1 Enrolment of Subjects (30 - 100 mg/kg Q3W) and Dose Escalation (Part II)

To ensure the safety of the study subjects, the first three subjects at and above the 30 mg/kg dose level will be enrolled stepwise after each has cleared their 28 day DLT observation period. The detailed rules for enrolling the first three subjects on a dose level are described below (4.3.2). If any of the first three subjects dosed at the 30 mg/kg dose level has a DMC verified DLT (see [Section 4.1](#) for DLT definition) within 28 days from the first IMP administration, an additional three subjects will be enrolled on the 30 mg/kg dose level. If a maximum of one of the six subjects experiences a DLT at 30 mg/kg dose level, up to ten subjects will be included in the 30 mg/kg dose level after which the trial can proceed to the next dose level. If at least two of the first three subjects or two of the six subjects experience a DMC verified DLT at the 30 mg/kg dose level, then the MTD has been reached, enrolment to the 30 mg/kg dose level will be placed on hold and dose escalation is terminated. The MTD is defined as the highest dose level, in which the first six subjects were treated with a maximum of one subject experiencing a DLT. Subjects on treatment who have not experienced DLT at that dose level may continue receiving the treatment and the DMC will decide regarding the treatment continuation and possible dose level de-escalation for these particular and DLT experienced subjects. The doses 45 and 100 mg/kg Q3W have the same 3 + 3 dosing rules as described for 30 mg/kg, and if at least two of the first three subjects or two of the six subjects has a DLT, then the MTD has been reached, enrolment to the dose level will be placed on hold, and dose escalation is terminated. If MTD is achieved at the dose level of 30mg/kg Q3W, a reserve de-escalation dose level of 20 mg/kg Q3W may be investigated with the same 3+3 design approach.

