- The proportion of lymphocyte subsets (CD4, CD8, their ratio, NK-cells, B-cells and regulatory T-cells, and macrophage HLA expression and myeloid derived suppressor cell populations in circulation will be analysed at given time points with flow cytometry and plotted against the scheduled sampling time. The level of circulating cytokines and chemokines (including but not necessarily limited to IFN γ , IL-1 β , IL-2, IL-4, IL-6, IL-8/CXCL8, IL-10, IL-12p70, IL-13 and TNF alpha, IP-10/CXCL10, Eotaxin/CCL11, MCP-1/CCL2, MIP-1 α /CCL3, MIP-1 β /CCL4) will be analysed by multiplex assays prior to and during the treatment. Aggregated data (mean and median) from each dose level will be presented using descriptive statistics.
- LDH, LDL and oxLDL, CRP, CA-125 (OC subjects), CA19-9 (PDAC, cholangiocarcinoma subjects), CEA (CRC subjects) and AFP (HCC subjects) levels prior to and during the treatment will be measured from blood.
- The ORR to the treatment will be determined by tumour imaging according to RECIST 1.1. The CBR is the proportion of subjects that have a CR, PR, or SD. The irORR will also be calculated. Results from each tumour type will be reported separately.
- The duration of response is measured from the time of initial response until documented tumour progression, death, or dropout.
- Progression free survival as the time from subject allocation into the trial until documented disease progression according to RECIST 1.1 or death will be measured in the population that has been dosed at least once.
- Overall survival is defined as the time from subject allocation into the trial until death from any cause and will be measured in the population that has been dosed at least once. Data will be censored on the last documented data that the subject has been alive.

Part II

Primary outcome measures

- Safety and tolerability will be defined by physical examination, adverse events and by safety laboratory tests. Adverse events are collected, graded and reported according to the NCI-CTCAE version 5.0. MedDRA terminology will be used to classify, record, manage, and analyse the data. Tolerability of new dose(s) will be determined based on the occurrence/non-occurrence of DLT during 28 days following the first dose of FP-1305 in subjects evaluable for DLT assessment in Part II.

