4.1 Dose Limiting Toxicity

DLT evaluable subjects include:

- Part I: All subjects
- Part II: The first three (or six if there is one DLT in the first three) subjects in the following cohorts
 - Q3W cohorts at dose levels that have not previously been tested in Part I
 - Q2W cohorts at each new dose level for the Q2W schema
 - Q1W cohorts at each new dose level for the Q1W schema
- Part III: DLT not applicable

DLT assessment period in Part II is shorter than in Part I, justified by the safety and tolerability data collected during the trial and enabling prompt dose escalation as a part of the 3+3 design of Part II.

- Part I: 63 days (9 weeks) following the first dose of FP-1305
- Part II: 28 days (4 weeks) following the first dose of FP-1305

A DLT is defined as a drug related AE \geq Grade 3 according to NCI-CTCAE version 5.0 occurring during the DLT assessment period and related to FP-1305. The following are exceptions to the rule:

- Grade 3 infusion reactions that resolve within 8 hours from the onset of the reaction are not defined as a DLT
- Grade 3 nausea/vomiting or diarrhea for less than 72 hours with adequate antiemetic and other supportive care are not defined as a DLT
- For thrombocytopenia, haemorrhage is required to qualify grade 3 toxicity as DLT; Grade 4 thrombocytopenia is DLT regardless of haemorrhage
- For neutropenia DLT is as follows,
 - Any neutropenic fever
 - Grade 3 neutropenia persisting $>$ 5 days or Grade 4 neutropenia
- For toxicity judged to be consistent with an acute infusion-related reaction or cytokine release syndrome, DLT will be defined as follows (Sehn 2012):
 - Grade 4 drug-related AE or
 - Grade 3 drug-related AE that cannot be resolved by infusion rate reduction or interruption, or supportive care.
- An AE which, in the opinion of the Investigator, is attributed to a study subject's underlying disease will not be considered a DLT.

In addition, the following are considered DLTs (occurring during the DLT assessment period and related to FP-1305):

- Grade ≥ 2 ALT or AST increase accompanied with bilirubin elevation $>2x$ ULN if baseline value was normal; $>2 \times$ baseline if baseline value was abnormal
- Dose delay of the 2nd cycle due to drug-related toxicity of >14 days

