4.3.2 Dosing Rules (30 - 100 mg/kg) (Q3W, Part II)

Sentinel dosing will be applied for 30-100mg/kg dosing. The second subject on a particular dose level can receive the first dose only after the first subject has been followed up for 28 days (additional precaution compared to traditional 3+3 model) after the first dose, and has not demonstrated any DLT. The third subject may receive the first dose after the second subject has been followed up for 28 days after the first dose and and neither of the subjects have demonstrated any DLTs. DLT evaluable subject will have at least one dose of IMP and have at least 28 days of follow-up after IMP infusion. If these criteria are not met, the subject will be replaced. Once three evaluable subjects have received at least one dose and have been followed up at for 28 days with no DLTs, all remaining subjects on the dose level may be enrolled without any hold. If any of the first three subjects cannot be followed for the full 28-day DLT observation period for reasons other than DLT, the subject may be replaced in order to obtain the required tolerability information of 28 days from the first IMP infusion, before the remaining subjects on the dose level may be enrolled. The replaced subject will, however, count towards the cohort of 10 subjects. The same rules will apply for the other dose levels.

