15.1 Trial Population

The trial subject population includes subjects who have advanced (inoperable or metastatic) cutaneous melanoma, pancreatic ductal adenocarcinoma, ovarian cancer, colorectal adenocarcinoma, hepatocellular carcinoma, gallbladder cancer, cholangio-carcinoma, uveal melanoma, gastric (including GE junction) adenocarcinoma, ER+ breast cancer and anaplastic thyroid cancer without standard treatment options available and who adhere to the trial inclusion and exclusion criteria.

For the purpose of analyses the following populations are defined:

Safety population: Includes all subjects who have received any amount of FP-1305

DLT evaluable population: Includes all subjects in Part I who have received at least one dose of FP-1305 and followed up for at least three weeks. Any subject that withdraws, discontinues from the trial or dies not related to treatment prior to the end of the 9-week DLT assessment period will be replaced.

Efficacy evaluable population: Includes all subjects who have received at least one dose of FP-1305 for the first time and has tumour imaging conducted at the baseline, and at least once during the treatment or progress or die due to their disease before the first tumour imaging post FP-1305 administration.

Subjects that re-initiate the treatment: Includes all subjects that have received at least one dose of FP-1305 after re-initiation of the therapy and has tumour imaging conducted at the baseline, and at least once during the treatment or progress or die due to their disease before the first tumour imaging post FP-1305 administration will be analysed for efficacy after the re-initiation in a separate cohort.

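### Section 4.1 and the Part II SAP drop subjects 4–6 from the DLT count after 0/3, while the MTD definition in 4.3.1 counts the first six, so the same data can pass one rule and fail the other

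*Protocol*

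**What the plan says.** **Who counts for DLT.** Protocol 4.1 lists the DLT-evaluable subjects as "Part II: The first three (or six if there is one DLT in the first three) subjects in the following cohorts" that test a new dose or frequency. Part II SAP section 8 repeats this: three subjects, expanded to six if one of the three has a DLT.

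Protocol 4.3.1 defines the MTD as "the highest dose level, in which the first six subjects were treated with a maximum of one subject experiencing a DLT", with no condition on the first three. Section 4.2.5, on delayed toxicity, also takes six: "In case two delayed DLTs occur in the first 6 subjects (DLT evaluable patients) at a particular dose". Section 4.3.2 describes an evaluable subject by one dose and 28 days of follow-up, with no limit on position in the cohort. Section 15.1 does not settle the matter, because the set it defines for DLT is limited to Part I: "Includes all subjects in Part I who have received at least one dose of FP-1305 and followed up for at least three weeks".

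The Part II primary tolerability outcome (3.10) rests on "occurrence/non-occurrence of DLT during 28 days following the first dose of FP-1305 in subjects evaluable for DLT assessment in Part II".

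**When the next level opens.** Section 4.3 says "To ensure safety at high doses the 30 mg/kg Q3W dose level will finish enrolment of all 10 subjects before the" step to 45 mg/kg, and sets the same condition for 45 to 100 mg/kg. Section 4.3.1 says "up to ten subjects will be included in the 30 mg/kg dose level after which the trial can proceed to the next dose level". The first three subjects are each separated by 28 days. After three clear without a DLT, 4.3.2 says "all remaining subjects on the dose level may be enrolled without any hold".

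**The concern.** After 0/3, subjects 4–6 are outside the DLT set under 4.1 and the SAP but inside the MTD definition. If two or three of them have a DLT, the level has cleared the 3+3 as 4.1 counts it and escalation is open, yet the same level cannot be called the MTD. The denominator of a primary tolerability outcome, three or six, then depends on which section is followed.

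Section 4.2.5 makes the mismatch plainer. Two DLT-type events in the first six that occur after day 28 halt enrolment. If both fall in subjects 4–6 after 0/3 and occur within the 28 days, 4.1 applies no count to them.

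A smaller matter is that the ten-subject condition is offered as a safety measure but is met by enrolment. No rule asks the later subjects to finish their 28-day window before the next level opens.

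**Working it through.** The documents state no operating characteristics for the Part II 3+3, so there is no figure to reproduce.

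**Inputs.** The rules come from 4.1, 4.3.1 and SAP section 8, and the window is 28 days (4.1). The true 28-day DLT rate p at these doses is not given. I assume 5 to 40%. For context, the Part I target was 20% (section 4), and no DLT was recorded at 0.1–10 mg/kg (2.6.3). Let q = 1 − p.

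**Step 1: clearance under 4.1.** A level passes on 0/3, or on 1/3 followed by 0/3:
A = q³ + 3pq² × q³ = q³ + 3pq⁵.

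**Step 2: clearance under the first-six rule.** A level passes with at most one DLT in six:
B = q⁶ + 6pq⁵.

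**Step 3: the two rules disagree.** This needs 0/3, then at least two DLTs in the next three:
A − B = q³ × (3p²q + p³).

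| p | q³ | P(≥2 of next 3) | Conflict (A − B) | Clears, 4.1 (A) | Clears, first six (B) |
|---|---|---|---|---|---|
| 5% | 0.857 | 0.007 | 0.006 | 0.973 | 0.967 |
| 10% | 0.729 | 0.028 | 0.020 | 0.906 | 0.886 |
| 20% | 0.512 | 0.104 | 0.053 | 0.709 | 0.655 |
| 30% | 0.343 | 0.216 | 0.074 | 0.494 | 0.420 |
| 40% | 0.216 | 0.352 | 0.076 | 0.309 | 0.233 |

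Worked line at 20%: 0.8³ = 0.512; 3 × 0.04 × 0.8 + 0.008 = 0.104; 0.512 × 0.104 = 0.053.

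**Step 4: open windows at escalation (secondary).** Assume 0/3, then one subject a week, the next level opening on the day the tenth subject is first dosed, and DLT onset uniform over 28 days. Four windows are open, at 0, 7, 14 and 21 days since first dose. A subject at u days has a DLT still to come with probability p(1 − u/28).

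- At 10% these probabilities are 0.100, 0.075, 0.050 and 0.025. P(at least one) = 1 − 0.900 × 0.925 × 0.950 × 0.975 = 0.23. P(two or more) = 0.02.
- At 20% they are 0.20, 0.15, 0.10 and 0.05. P(at least one) = 1 − 0.80 × 0.85 × 0.90 × 0.95 = 0.42. P(two or more) = 0.08.

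**The case against.** **On who counts.** In 4.3.1, permission to proceed is tied to at most one DLT in six, and termination to two of six. Read with the MTD sentence beside them, these could mean that 0/3 followed by two DLTs stops the level, so 4.3.1 is coherent on its own. That reading is available, but the six-subject sentences follow the instruction to add three subjects after a DLT, so they can equally be read as 4.1 reads. Section 4.1 and the SAP say outright that six applies only after a DLT. The objection shows that one reading is safe; it does not show that the documents choose it. It is also fair that the conflict is uncommon, at about 5% or less for true rates up to 20%.

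**On the gate.** A conventional 3+3 would allow escalation once three subjects clear. This protocol adds 28-day spacing of the first three and a cohort of ten. A reader might infer that the trial escalates unsafely, with up to seven subjects unobserved. The documents do not support that:
- Sentinel dosing at the next level (4.3.2) means about one subject receives the higher dose while the last windows close.
- Sites report DLTs within 24 hours (4.1).
- The DMC reviews toxicity when a DLT is observed and can recommend stopping escalation (17.2).
- Escalation is permitted, not required.
- One pending DLT after 0/3 breaches no rule, so the 0.23 and 0.42 above overstate what bears on a decision.

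What stands is narrower: no text requires complete 28-day data on the cohort before the next level.

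**On reporting.** A reader might also take the lack of a DLT table in the Part II SAP's table plan as an omission. Protocol 15.3.4.5 already commits to separate tabular DLT reporting, section 15 allows later SAP subversions, and the present SAP mainly reports the originally enrolled Q3W cohorts at doses already tested in Part I.

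**Conclusion.** The inconsistency holds. Section 4.1 and SAP section 8 give one denominator after 0/3, and the MTD definition in 4.3.1, supported by 4.2.5, gives another. The two disagree with probability 0.006 to 0.08 across assumed true DLT rates of 5 to 40%. Clearance at 10, 20 and 30% is 0.91, 0.71 and 0.49 under 4.1, against 0.89, 0.66 and 0.42 under the first-six rule. These figures assume independent DLTs at a common rate, and the rate is an assumption because the documents give none for 30–100 mg/kg.

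The enrolment-based gate is true to the text but secondary, and closing it brings a modest benefit. Severity is minor. The Q2W and Q1W addendum was not available, so the point is shown for Q3W only.

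**What to change.** **Main change.**
- In 4.1 and SAP section 8, make the first six subjects at each new Part II dose level DLT-evaluable for 28 days, whatever happens in the first three.
- In 4.3.1, state that two or more DLTs among the first six stop enrolment and escalation at that level, even after 0/3.
- Keep 0/3 as the rule that releases further enrolment, so accrual is not slowed.

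The consequence is slightly fewer levels clearing: 0.91 to 0.89 at a true 10%, and 0.71 to 0.66 at 20%.

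**Secondary change.** In 4.3 and 4.3.1, require that every subject at the current level has completed 28 days, had a DLT or left for a documented reason, and that the DMC has seen the cumulative DLT count, before the next level opens.

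**Cost.** A protocol amendment, with authority and ethics approval where needed (section 13), and SAP wording. The secondary change adds up to about four weeks after the tenth subject's first dose and one DMC look at each remaining gate. There are at most two gates, since 45 mg/kg is optional (2.6.3). No extra subjects or visits are needed. Part II SAP section 4 describes the 30 mg/kg cohort as recruited, so the change may apply mainly to later levels.
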